
March 2020 Update:

In consultation with the NIMHD, in March 2020 the Investigators expanded the recruitment area to include the entire United States in order to assist with meeting recruitment targets by age and race/ethnicity.

2. Key Inclusion Criteria:

Inclusion criteria for enrollment into the study include:

1. being assigned a male sex at birth and identifying as male at time of enrollment,
2. being between the ages of 13-18 (inclusive),
3. speaking and reading English,
4. reporting same-sex attractions and/or behaviors,
5. have access to the internet,
6. living in and the United States
7. self-report as HIV-negative at time of enrollment.

Additionally, given that this is an online intervention, in order to be considered enrolled in the study, individuals must complete enrollment procedures which include

- providing and verifying contact information, and
- passing fraud checks described in the screening and data management sections of this protocol.

After these criteria have been met, participants will be randomized into a study arm and considered enrolled into the study.

Eligibility will close as goals are filled.

Justification. Socially disadvantaged populations in the United States (e.g., individuals who identify as racial/ethnic and/or sexual minorities, live in poverty, and/or reside in underserved communities) are more vulnerable to HIV infection and account for a substantial proportion of new HIV cases in the United States. These HIV disparities are further exacerbated when individuals are part of multiple minorities (e.g., Latino and MSM), as they may experience marginalization from both their racial/ethnic *and* sexual communities. These processes of marginalization may impact individuals' social mobility, create stress and social isolation, promote the adoption of negative coping behaviors (e.g., substance use), and disrupt access to community resources and social capital. Marginalization may also affect their sexual networks by limiting access to HIV prevention services, hindering their ability to enact safer sex practices when meeting partners, and shaping norms regarding risks. Youth, in particular, may experience further marginalization if they encounter structural policies that limit their development (e.g., absence of comprehensive sex education; no condoms in school settings). Together, these multilevel processes exacerbate HIV vulnerability among AMSM.

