Materials will avoid identifying candidates as AMSM in the recruitment text to avoid unintended disclosure. Ads will link interested individuals to the study site where they may verify their eligibility, email the team, or locate a toll-free number if they want to talk to a team member about the study. AMSM will click on viewed social media advertisements and be taken to a homepage containing basic study information including a short description of study activities. The homepage will not identify the study as a site for MSM.

Screening: Interested individuals will be asked to consent to and complete an online screening survey. We will use this approach as one of our strategies for filtering fraudulent or duplicate entries (see Measures to protect against fraud and hacking below). Individuals who do not meet the eligibility criteria will be thanked for their interest and automatically routed to the Google home page. We will not indicate why they were ineligible to avoid unintentional disclosure and to protect against fraud. In order to meet recruitment sub-targets (e.g. by race/ethnicity), the eligibility screener programming will be modified to exclude groups as recruitment sub-targets are met. Participants who are part of these now-excluded groups and would otherwise be eligible to participate will be offered the opportunity to provide their contact information and be put on a study "waitlist." Individuals on this list may be re-contacted if recruitment targets are re-evaluated in the future. **Consent:** If they are screened eligible, they will be taken to the study consent form (a waiver of parental consent has been obtained for minor participants). To optimize AMSMs active understanding of the consent process, we also include a video with subtitles and key concepts from the consent form at the bottom of the video screen. The video will be followed by the full consent form, which AMSM will be prompted to read and then either consent to or reject participation. AMSM will also have the ability to download a complete version of the consent form. AMSM who do not consent will be taken to a screen thanking them for their interest (which will also include information on HIV testing). AMSM who consent to participate will be directed to continue through the registration process.

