The research activities involve a two-arm prospective RCT enrolling a sample of 600 AMSM with the aim of maintaining a randomized sample of approximately 500 online-recruited AMSM (13-18), assuming 15-20% attrition. After consent and completion of the online baseline survey, AMSM are randomized to either the control or experimental condition (Intervention, n=300; Control, n=300). Participants in the control arm will receive access to only the resource locator function of iReach, allowing them to search for local resources. Participants recruited nationally will receive a list of national resources. Participants in the experimental arm will receive access to all iReach functions, including life skills education, goal setting, local/national resource directory, a discussion forum related to life skills and goal setting, and the ability to link to a Peer Mentor through the VSee video-chat function. After consent and a baseline survey, AMSM are randomized to either the attention control or intervention condition. Self-completed study assessments are conducted online every three months across the intervention and attention-control follow-up time points, with a total follow-up period of 12 months for participants initially randomized into the intervention group, and 15 months for participants initially randomized into the control group. In months 12 to 15, we will make the intervention accessible to AMSM in the attention-control condition. The primary outcomes are cognitive (e.g., HIV prevention attitudes, norms, self-efficacy, behavioral intentions); behavioral outcomes are secondary (e.g., condom use, HIV testing, PrEP use). The proposed study design thus tests the impact of an e-delivered life skills intervention with an embedded video-chat peer motivational interviewing function on cognitive and behavioral HIV-related outcomes on a large (n=600) sample of AMSM.

The study is funded for approximately 5 years (Project Period: 07/28/2016 to 02/28/2021). Once consented, participants randomized into the intervention group will be active in the study for 12 months. Participants randomized into the control group will be active in the study for 15 months.

METHODS:

1. Study Instruments:

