The research activities involve a two-arm prospective RCT enrolling a sample of 600 AMSM with the aim of maintaining a randomized sample of approximately 500 online-recruited AMSM, assuming 15-20% attrition. After consent and completion of the baseline survey, AMSM are randomized to either the control or experimental condition (Intervention, n=300; Control, n=300). Participants in the control arm will receive access to only the resource locator function of iReach, allowing them to search for local/national resources. Participants in the experimental arm will receive access to all iReach functions, including life skills education, goal setting, a discussion forum related to life skills and goal setting, local/national resource directory, and the ability to link to a peer mentor through the VSee video-chat function. Self-completed study assessments are conducted online every three months across the intervention and attention-control follow-up time points, with a total follow-up period of 12 months. At the end of the trial, we will make the intervention accessible to AMSM in the attention-control condition for a 3 month period, followed by an additional follow-up assessment at month 15. The primary outcomes are cognitive (e.g., HIV prevention attitudes, norms, self-efficacy, behavioral intentions); behavioral outcomes are secondary (e.g., condom use, HIV testing, PrEP use). The proposed study design thus tests the impact of an e-delivered life skills intervention with an embedded video-chat peer motivational interviewing function on cognitive and behavioral HIV-related outcomes on a large (n=600) sample of AMSM.

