Measures to protect against fraud and hacking: We will use best practices to reduce the likelihood of online fraud: (1) Keep compensation sufficiently low (i.e., balance incentives with the effort required from respondents) to reduce the chances of respondents participating solely to gain incentive payments. (2) Verify contact information using multiple verification methods, including email, cell phone, and mailing address. The validation, or verification, of participant contact information is the "gold standard" for fraud prevention. This process (see above) is commonly used in online research and will prevent multiple submissions as well as help ensure that the intended participant fills out the responses. We will verify participant information using two forms of personal information, including their mobile phone, to ensure that the participant's mobile phone number is unique in the study database. (3) Run duplicate detection software: we will continually run duplicate detection software (i.e., respondent creates a fake user profile to gain incentives) until recruitment is complete and all subjects are verified.

Experimental Group: iReach is a tailored intervention for AMSM. The intervention component of the app aims to facilitate users to lower their vulnerability to HIV infection by (1) providing life skills educational modules tailored on their unique needs and characteristics, (2) setting goals and encouraging participants to use relevant services available locally to help achieve them, (3) accessing LGBTQ-welcoming resources across. The life skills educational content in iReach covers 14 topics and includes resources tied to these topics (e.g. housing, transportation, education, HIV testing and care sites) in their region or national directories to find local resources. The intervention content is written at the 8th grade literacy level. Among newly diagnosed HIV cases, iReach will provide HIV-specific content (e.g., how Ryan White funds can assist with housing and transportation, social support, etc.). Tailored electronic content is based on AMSM's baseline assessment, with opportunities to have new content personalized based on AMSM's answers to the follow-up surveys and as new information/research findings become available. Content is tailored on characteristics collected at baseline (e.g., age,

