Not applicable.

5. Statistical Analysis:

Descriptive statistics of the psychosocial and demographic characteristics of the participants will be described for all and by intervention group. These will be compared between treatment groups using t-tests or Wilcoxon rank sum tests for continuous variables and chi-square tests for categorical variables. In addition, we will use the general framework of generalized linear mixed models (GLMM) to test for intervention effects over time. Note that some of our outcomes are binary, some count and some continuous traits and thus need to be treated differently. The general form of the GLMM will be $\mu_{ij} = \beta_0 + \beta_1 \text{cov} + \beta_2 \text{Time} + \beta_3 \text{InterventionGroup} + \beta_4 \text{Group} \times \text{Time}$, where μ_{ij} is the mean response corresponding to subject i at Time j (baseline and 4 follow-ups) with the appropriate link function (identity for continuous outcome, logit for binary outcome and natural log for count outcomes); Group = 1 if the i -th subject is in the intervention group and 0 if the i -th subject is in the attention-control group. The interaction coefficients β_4 (Group \times Time) are of interest here, measuring the difference in the rate of change in outcomes across the two treatment groups over time. The subject-specific random intercepts β_0i are assumed to be normally distributed with a common variance and they account for within-person correlation. We will also explore if we need a subject specific random-slope corresponding to visit in the above model. Maximum likelihood estimation will be used for fixed effect parameters. Models will be compared according to information criterion like AIC, BIC. For some binary outcomes like HIV testing, we will perform an aggregate analysis after collapsing across the repeated measures using simple logistic regression comparing whether the probability of having tested at least once over the entire FU period is different across treatment groups, after adjusting for baseline values. To ensure robustness, we will also apply an exchangeable working correlation structure to its corresponding generalized estimating equation (GEE) model. We will also conduct exploratory regression analyses to examine differences based on social determinants of interest: age group, race/ethnicity, and rurality. These regressions will be run with group assignment and the social determinant variables of interest in the models, controlling for region. Interactions between group assignment and these social determinants will be tested to explore potential group-specific moderators of treatment effect. Given our focus on disparities, we also intend to examine mean differences across sub-groups of interest (e.g., race/ethnicity, developmental age group, urban vs. suburban vs. rural). For example, assuming we used a fixed effects ANOVA model with main effects and interactions by race and intervention condition, we would be able to detect any interaction effect size f of .18 in cross-sectional analyses at 80% power using a two-sided significance level of .05. Similar interaction effect sizes are obtained for developmental age (i.e., early (ages 13-14) vs. middle (ages 15-16) vs. late (ages 17-18) adolescence) and rurality (i.e., urban vs. sub-urban vs. rural). Secondary Analyses: Building on our GLMM framework employed for Aim 2, we will examine whether there are intervention effects in the socioecological factors (e.g., LGBT discrimination; HIV stigma) and life skills components (e.g., personal competence; identity development) associated with our outcomes. The regressions will be run with group assignment only in the model, as well as controlling for participants socio-demographic characteristics, psychological distress, and intervention-related process data (e.g., frequency of use, acceptability). In addition, we will test whether these relationships vary as a function of AMSMs varying engagement with the intervention (e.g., dose analysis; intervention acceptability, frequency of site log-ins; time spent on sites and modules; number and length of VSee sessions used). Interactions between group assignment and these characteristics will be tested to explore potential moderators of treatment effect. Recognizing that social determinants operate beyond the individual-level, we will use HLM to test how regional characteristics influence AMSMs outcomes. HLM allows us to take into account that participants are nested within regions, and examine whether regional characteristics are associated with individual-level outcomes. We will link individual and regional level data using participants residential address at enrollment. Some participants may be residentially unstable and/or would not want to give their exact location. We will estimate a two-level model to account for individual and regional variation.

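### The exploratory moderator models only control for region, so a different intervention effect in national recruits could be read as moderation by race/ethnicity or age

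*Protocol*

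**What the plan says.** **Who is recruited nationally.** The March 2020 Update in the protocol's Characteristics of the Study Population records that "the Investigators expanded the recruitment area to include the entire United States in order to assist with meeting recruitment targets by age and race/ethnicity". Under Subject Recruitment and Screening, "the eligibility screener programming will be modified to exclude groups as recruitment sub-targets are met". National recruits are treated as a fifth region and randomised 1:1 (Methods, Method for Assigning Subjects to Groups).

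**What they receive.** The protocol's Study Design section states, directly after describing the control arm: "Participants recruited nationally will receive a list of national resources". The Detailed Description under Study Procedures gives the control arm "access to only the resource locator function of iReach, allowing them to search for local/national resources". It lists among the experimental arm's functions a "local/national resource directory, and the ability to link to a peer mentor through the VSee video-chat function". The Experimental Group paragraph describes resources "in their region or national directories to find local resources".

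**How moderation is analysed.** Study Procedures, section 5 (Statistical Analysis), plans exploratory regressions on age group, race/ethnicity and rurality, with group-by-determinant interactions. On region: "These regressions will be run with group assignment and the social determinant variables of interest in the models, controlling for region". No group-by-region or group-by-national term is named, either there or in the hierarchical model for regional characteristics.

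**The SAP.** Its Scope, General Study Design and Inclusion-Exclusion sections still describe four regions. It mentions no national stratum and sets out no moderator model.

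**The concern.** National status is expected to be associated with race/ethnicity and age, because the expansion was made to fill those targets and the screener closes to groups already filled. National recruits also enrol only from March 2020 and have a different resource component.

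The arm contrast could differ between national recruits and the four original regions because the resource component plays a different part in each arm:

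- In the control arm it is the whole condition. The protocol itself calls it a weak intervention that may reduce the detectable effect (Attention Control Condition).
- In the experimental arm it is tied to other functions. Verified listings are mapped to life-skills goals, the pre-set goals include one that sends users to the locator, and mentors use it to find local services.

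A region main effect adjusts outcome levels by region. It leaves any regional difference in treatment effect to be absorbed by whatever interaction is in the model, here group by race/ethnicity or group by age.

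What is at stake is attribution. Aim 4 asks how individual determinants such as race/ethnicity relate to efficacy, and the Background suggests larger gains in disadvantaged groups. A gap due to recruitment source could be reported as a race/ethnicity or age difference, or could mask a real one.

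**Working it through.** **The plan's own interaction figure.** The protocol states a detectable interaction of f = 0.18 at 80% power, two-sided 0.05. For a fixed-effects interaction with N = 500 and three levels (age group or rurality; noncentral F, λ = f²N, df 2 and 494), the detectable f is 0.139, and power at 0.18 is 95.8%. The number of race levels is not stated; 4 to 7 levels give 0.148 to 0.166. So 0.18 is not reproduced from these inputs. It is conservative, and the point here does not depend on it.

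**Bias formula.** Let δ be the arm contrast in national recruits minus that in the four original regions, and let pA and pB be the shares of determinant groups A and B recruited nationally. With 1:1 allocation within strata and no true moderation, the arm contrast is θ + pA·δ in group A and θ + pB·δ in group B. The spurious interaction is δ(pA − pB).

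**Standard error.** Take N = 500 (the protocol's analysis sample), two equal determinant groups of 250 (assumed), outcome SD 1 and 1:1 arms. The variance of the arm contrast in a group of size n is 4/n. The interaction variance is 4/250 + 4/250 = 0.032, so the SE is 0.179 SD.

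**Cost of adding group by national.** The interaction variance is multiplied by 1/(1 − r²), with r² = (pA − pB)² × 0.25 / [p(1 − p)]. The overall national share p is 0.40 in all three scenarios, which gives r² = 0.042, 0.167 and 0.375, and multipliers of 1.04, 1.20 and 1.60.

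The documents give neither δ nor the national shares. All values in the first two columns are assumptions.

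| National share, A v B | δ (SD) | Bias (SD) | Bias/SE | False-positive rate | SE with added term | Added variance | Squared bias removed |
|---|---|---|---|---|---|---|---|
| 50% v 30% | 0.05 | 0.01 | 0.06 | 5.0% | +2% | 0.0014 | 0.0001 |
| 60% v 20% | 0.10 | 0.04 | 0.22 | 5.6% | +10% | 0.0064 | 0.0016 |
| 70% v 10% | 0.15 | 0.09 | 0.50 | 8% | +26% | 0.0192 | 0.0081 |

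For a balanced two-level determinant, f is the interaction divided by 4. The largest bias is therefore f = 0.09/4 = 0.0225, one eighth of the stated 0.18.

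**Wider assumptions.** With δ = 0.3 and a share difference of 0.5, the bias is 0.15 SD and the false-positive rate 13%. With δ = 0.5 and the same share difference, they are 0.25 SD and 29%. If δ = 0, the bias is zero whatever the shares.

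**Simulation check.** With 4,000 replicates, N = 500, five regions and shares of 60% v 10%, δ = 0.3 gave a mean spurious interaction of 0.150 and 13.2% rejections. Adding group by national brought these to 0.000 and 5.3%.

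**Cost of restricting to the four regions.** Under the tabulated shares, 300 of 500 participants remain, split 125/175, 100/200 or 75/225. The SEs are √(4/125 + 4/175) = 0.234, √(4/100 + 4/200) = 0.245 and √(4/75 + 4/225) = 0.267. These are about 31%, 37% and 49% above 0.179.

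**The case against.** The best defence is that the resource function goes to both arms and that the protocol defines the contrast under test as life-skills content plus peer mentoring. A change common to both arms cancels unless it interacts with those parts. The primary outcomes are cognitive, and nothing in the documents shows that the format of a resource list alters the contrast on them. This stands as a reason for caution about size. It does not make δ zero, given how differently the locator is used in the two arms.

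The models are also labelled exploratory, and the largest tabulated bias is about half a standard error. Both points stand. They argue for sensitivity analyses rather than replacement of the planned models. In all three scenarios the added term brings in more variance than the squared bias it removes, so reading results only from the expanded model would raise the mean squared error there.

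A reader might infer several stronger claims that the documents do not support:

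- **That the moderator tests are confounded.** This is possible but not shown. The national shares by race/ethnicity and age are not given, nothing says that recruitment in the four regions stopped in March 2020, and screener closure is not limited to national recruits.
- **That national recruits lose access to local services or receive a second intervention.** The Detailed Description gives both arms local/national resources, and the national directories are described as a route to local ones.
- **That Aim 4 names age.** Its individual-level examples are race/ethnicity and urbanity. Age enters through the sampling rationale and the exploratory regressions.
- **That the primary effect is biased.** Allocation is 1:1 within the national stratum, so this mechanism does not bias the overall comparison.

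**Conclusion.** The point holds as a limit on attribution in the exploratory moderator analyses. As ordinarily read, controlling for region means a main effect, and that cannot absorb a difference in arm contrast between national recruits and the four original regions. Because national recruitment was opened for age and race/ethnicity targets, part of any such difference can be assigned to those determinants.

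The size is unknown. Under the tabulated assumptions it is 0.01 to 0.09 SD against an SE of about 0.18 SD, with a false-positive rate of about 5% to 8%. Rates of 13% or more need effect differences of at least 0.3 SD together with widely different national shares. The result rests on two equal determinant groups, 1:1 allocation within strata, N = 500, and assumed values for both the shares and the effect difference.

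**What to change.** Keep the planned moderator models. Pre-specify two sensitivity analyses for age group, race/ethnicity and rurality:

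1. the same models with a group-by-national-stratum term added;
2. the same models in participants from the four original regions only.

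Attribute differential efficacy to a determinant only if its estimate is consistent across the planned model and both sensitivity models. Judge consistency by direction and approximate size, not by whether each reaches significance, because both sensitivity models are less precise. Report the national share by race/ethnicity, age group and rurality so that the possible bias can be judged.

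Add the national stratum to the SAP's study design, eligibility and randomisation sections, and set out the moderator models there.

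The cost is wording and a few extra model fits. No new data are needed, because the fifth region is already used for randomisation. Under the assumed shares, the interaction SE is about 2% to 26% larger with the added term and about 31% to 49% larger in the four-region analysis.

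### The exploratory moderator regressions name no visit and no baseline adjustment and are not tied to the Group x Time effect; a baseline-adjusted month-12 interaction would be clearer and more precise

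*Protocol*

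**What the plan says.** All of the relevant text is in the protocol, Study Procedures, section 5 (Statistical Analysis).

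- **Efficacy.** The mixed model uses "baseline and 4 follow-ups" as response times. Its Group x Time coefficients are the effect of interest, "measuring the difference in the rate of change in outcomes across the two treatment groups over time".
- **Moderators.** The plan then turns to a further set of models: "We will also conduct exploratory regression analyses to examine differences based on social determinants of interest: age group, race/ethnicity, and rurality". Their content is given as "These regressions will be run with group assignment and the social determinant variables of interest in the models, controlling for region", and the test as "Interactions between group assignment and these social determinants will be tested to explore potential group-specific moderators of treatment effect".
- **Power.** The example is a fixed-effects ANOVA with race and condition, said to "detect any interaction effect size f of .18 in cross-sectional analyses at 80% power using a two-sided significance level of .05". Similar sizes are claimed for rurality (three levels) and for developmental age, defined as "early (ages 13-14) vs. middle (ages 15-16) vs. late (ages 17-18) adolescence".

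The moderator text does not say which visit or visits supply the outcome, whether the baseline score is a covariate, or whether any term involves Time. The SAP restates Aim 4 and lists moderators under Covariates and Subgroups, but its Efficacy Analyses section contains no moderator model.

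**The concern.** Efficacy is defined through change over time, but the moderator test is a two-way interaction without Time. What that interaction measures depends on the model it sits in. At a single follow-up visit it is the subgroup difference in the between-arm contrast. In a model where baseline is one of the responses, it averages that difference over all waves, including one where randomisation makes it zero in expectation.

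Differential efficacy is Aim 4. The protocol's Background expects that disadvantaged groups may gain more and says this will be tested. If the model is left open, the choice can be made after the data are seen, and no reading of the listed terms uses the baseline score as a covariate although it is collected.

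**Working it through.** **The plan's own figure.** For a Group x determinant F test, the noncentrality is f² x N. With N = 500 and a three-level determinant (2 degrees of freedom), the f detectable at 80% power is 0.139, and power at f = .18 is 96%. So .18 does not reproduce for the three-level age and rurality factors at N = 500; it would fit three levels at N of about 301. The number of race levels is not stated. The discrepancy is on the conservative side.

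**Inputs from the documents.** N = 500 analysed, 1:1 allocation, and within-person correlation ρ of 0.25 and 0.75 (protocol, Target Population and Accrual). Primary outcomes are scheduled at 0, 6 and 12 months, with month 15 outside the 12-month comparison (SAP, Study Assessments table).

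**Assumptions not in the documents.** Two equal subgroups, unit SD, compound symmetry, and an interaction δ at month 12 that is zero at baseline and either grows linearly or is fully present by month 6.

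**Effect and relative variance of each test** (required N is proportional to variance / effect²):

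| Test | Effect | Variance | ρ = 0.25 | ρ = 0.75 |
|---|---|---|---|---|
| Month 12, baseline-adjusted | δ | 1 − ρ² | 0.9375 | 0.4375 |
| Month 12, unadjusted | δ | 1 | 1 | 1 |
| All waves, two-way term, linear | δ x mean(0, ½, 1) = δ/2 | ρ + (1 − ρ)/3 | 0.5 | 0.8333 |
| All waves, two-way term, plateau | δ x mean(0, 1, 1) = 2δ/3 | ρ + (1 − ρ)/3 | 0.5 | 0.8333 |

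**Required N relative to the baseline-adjusted test:**

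- Month 12, unadjusted: 1/0.9375 = 1.07; 1/0.4375 = 2.29.
- All waves, linear: (0.5/0.25)/0.9375 = 2.13; (0.8333/0.25)/0.4375 = 7.62.
- All waves, plateau: (0.5 x 9/4)/0.9375 = 1.2; (0.8333 x 9/4)/0.4375 = 4.3.

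**Power at the plan's f = .18.** In a balanced 2 x 2 layout f = δ/4, so δ = 0.72 SD. The month-12 interaction has SE 4/√500 = 0.179.

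- Month 12, unadjusted: z = 0.72/0.179 = 4.02, power 98%.
- Month 12, baseline-adjusted: SE 0.173 and 0.118, power 99% and above 99%.
- All waves, linear: effect 0.36; SE 0.179 x √0.5 = 0.126 and 0.179 x √0.8333 = 0.163; power 81% and 60%.
- All waves, plateau: effect 0.48, same SEs; power 97% and 84%.

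Using all five visits under linear growth changes the all-wave power to 89% and 61%.

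**Three levels instead of two.** The N ratios do not depend on the number of levels. Power at f = .18 does. The month-12 noncentrality is 0.18² x 500 = 16.2 (power 96%). For the all-wave linear case it is 16.2 x 0.25/0.5 = 8.1 and 16.2 x 0.25/0.8333 = 4.86, giving about 72% and 49% on 2 degrees of freedom.

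**The case against.** The strongest reply is that the text points to a cross-sectional analysis. These regressions are introduced separately from the mixed model, list no Time term, and are followed by an ANOVA example described as cross-sectional. The next block, by contrast, expressly builds on the mixed-model framework. In a follow-up regression the named interaction is valid moderation. The same holds for the aggregate logistic analysis of outcomes such as HIV testing, which has no Time term and does adjust for baseline. All of this stands. It limits the loss under that reading to precision.

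It may also be said that silence about baseline is not omission. That is fair. But the plan states baseline adjustment explicitly for the aggregate logistic analysis and not here, so an analyst following the listed terms would leave it out.

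A reader might infer something stronger: that the planned test is not moderation of efficacy at all, or has almost no power. The documents do not support that.

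- Rejection at only 5% would require fitting Group x Time x determinant with baseline coded zero, under linear divergence, and then interpreting the two-way term. Neither document says this will be done.
- If the interaction is sized so that the baseline-adjusted test has exactly 80% power, the diluted term has about 48% (ρ = 0.25) and 17% (ρ = 0.75). At ρ = 0.75 that interaction is only 0.33 SD (f of about 0.083), less than half of what the plan claims to detect.

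**Conclusion.** The point holds as a specification gap with a precision cost, not as a wrong test. On the better-supported cross-sectional reading, the interaction is valid but needs 7% to 129% more participants than a baseline-adjusted test for the same power. On the all-wave reading, it recovers half to two thirds of the month-12 interaction and needs 1.2 to 7.6 times the sample. Power at f = .18 is then reduced but not lost.

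These sizes rest on compound symmetry, the assumed time course and a continuous outcome; the 60% to 81% power range also rests on two equal subgroups and linear growth. The analysis is labelled exploratory, so severity is minor. The regional part of Aim 4, handled by the hierarchical model, is outside this point.

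**What to change.** In the protocol, Study Procedures, section 5, replace the moderator-test sentence, and add the same text as a new statement in the SAP, Efficacy Analyses:

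*For continuous outcomes, moderation by age group, race/ethnicity and rurality is tested as Group x determinant on the month-12 outcome, adjusted for its baseline value and region (or as Group x Time x determinant if the repeated-measures mixed model is used). Binary and count outcomes use the matching baseline-adjusted model with the same interaction. A two-way Group x determinant term from a model with baseline as a response is not interpreted as moderation. These analyses are exploratory.*

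The sponsor should choose one of the two options for continuous outcomes before the data are analysed, since a month-12 contrast and a rate-of-change contrast are not the same quantity. The cost is a few lines in each document, with no new data and no change to the sample size.
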